- To compare the incidence of mesangial expansion >20% in patients treated with Exenatide SR + SOC vs. SOC alone at 24 months after kidney transplantation.
- To compare transplant kidney function in the two arms
- To compare the incidence of death by any cause in the two arms
- To compare the incidence of graft loss by any cause in the two arms.

Inclusion criteria:

- Recipients of solitary kidney transplants (i.e. not combined liver-kidney, pancreas-kidney etc.)
- Labs consistent with prediabetes, as determined at 4 and 12 months after transplantation: Prediabetes (fasting blood glucose 100-125 mg/dl; or 2 hr glucose 140-199 or HgbA1c 5.7-6.4%)

Exclusion criteria:

- Diabetes pre-transplantation
- Diabetes at 4 and 12 months
- <18 years of age
- eGFR <30 ml/min (estimated by MDRD equation from serum creatinine)
- Active acute cellular rejection including borderline (If treated and resolved, these patients can be included)
- BK nephropathy active
- History of pancreatitis, pre-existing moderate-to-severe gastroparesis, liver cirrhosis or family /personal history of multiple endocrine neoplasia 2 or medullary thyroid cancer
- Pregnant or breastfeeding women

Female Subject must be either:

- a. of non-child bearing potential
 - 1) Post-menopausal (defined as at least 1 year without any menses) prior to screening , or
 - 2) Documented surgically sterile or status post-hysterectomy
- b. Or if childbearing potential,
 - 1) Agree not to try and become pregnant during the study for at least 90 days after the final study drug administration.
 - 2) And have a negative serum or urine pregnancy test.
 - 3) And if heterosexually active, agree to consistently use two forms of highly effective birth control.

- Hypersensitivity to Exenatide

Criteria for Discontinuation of Medication:

- Decrease in renal function to eGFR to < 30 ml/min after study initiation
- Decrease in eGFR by 50% on the 2 consecutive measurements without otherwise identified cause which maybe correctable (like high immunosuppressive medication level, rejection, urinary tract infection, etc)
- Intolerable GI side effects despite the optimal therapy
- Thyroid tumor
- Pancreatitis
- Hypoglycemia

Study design/schedule

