This is a Phase 2, Prospective, Randomized, Multicenter, Open-Label, Controlled Trial. Patients are randomized to treatment with Exenatide SR + SOC vs. SOC alone at 4 months or 12 months post transplant after kidney transplantation and followed until 24 months after kidney transplantation. Patients who discontinued medication for AEs will be contacted within 30 days to follow up on the resolution of symptoms.

Study participants with prediabetes at 4 months or 12 months after kidney transplantation will be randomized 2:1 to receive either Exenatide SR or diet and exercise only with no medication. We plan to enroll approximately 50% of subjects at 4 months post transplant and 50% of subjects at 12 months post transplant

Primary Endpoint is the incidence of diabetes at 24 months after kidney transplantation.

Patients will be followed for 2 years after transplantation (20 or 12 months after enrollment) for progression to all endpoints. Therefore, there will be three SOC biopsies—4, 12 and 24 months after transplantation. Hemoglobin A1C will be performed at the same time points. In addition 2hOGTT will be performed if clinically indicated per our SOC.

Study Sites: This is a multicenter study involving the three Mayo Clinic kidney transplant programs. This group has a common IRB and can contract centrally. Collectively, they perform approximately 600 kidney transplants per year. They have a history of multicenter research trials—they enrolled 480 patients along with a fourth center in a recent NIH-sponsored trial that required a 1 year kidney biopsy (NCT01782586 Validation of Gene Expression Markers of Renal Allograft Functional Decline (<https://clinicaltrials.gov/ct2/show/NCT01782586?term=[name]&rank=10>)). Thus, this consortium is large enough to ensure enrollment in the time frame suggested, yet small enough to ensure collaboration and uniformity needed for these studies.

The patient visits and follow-up including safety laboratories all fall within the SOC follow-up at all sites. These include the biopsies. All clinical standard of care labs and biopsies are followed by clinical operating protocols and are followed by clinical nursing and physician staff.

Study drug:

Exenatide SR

Background.

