- To compare transplant kidney function in the two arms
- To compare the incidence of death by any cause in the two arms
- To compare the incidence of graft loss by any cause in the two arms.

Subject Safety

The consent process will inform a volunteer about the study, indicate that participation is voluntary and he/she has the right to stop at any time. Risks will be enumerated in the informed consent form and described orally during the consent process.

The potential risks to study participants include side effects of Exenatide SR (table 1) and medication interactions.

Table * Adverse Reactions Reported in ≥5% of Exenatide Extended Release Treated Patients with Type 2 DM in Monotherapy Trial

Symptom	Percent
Nausea	11.3
Diarrhea	10.0
Infection-site nodule	10.5
Constipation	8.5
Headache	8.1
Dyspepsia	7.3

*From the package insert

It will also inform volunteers about the rare more severe complications including: pancreatitis, renal impairment, hypersensitivity, C cell thyroid tumors (the risk in humans is not determined), development of antibodies to the medication, hypoglycemia when use with other medications for diabetes (oral or insulin)

DRUG INTERACTIONS

- May impact absorption of orally administered medications.
- Warfarin: Postmarketing reports with exenatide of increased INR sometimes associated with bleeding. Monitor INR frequently until stable upon initiation of BYDUREON therapy

Patients will be monitored for any drug interactions with immunosuppression and other medications. Immunosuppression levels will be monitored as outlined below. Recipients on Warfarin will be asked to monitor their INR through the local Anticoagulation Clinics or PCP as per patient's preference frequently and per local protocols until INR levels are stable.

Stopping Rules.

In general, the study drug is well-tolerated and we expect the same in kidney transplant recipients.

Enrollment will be suspended for any of the following:

- 2 hospital admissions that are deemed related to study drug
- A patient death in the study arm. This will be investigated for possible causal relation to study drug.

In addition, the investigator also has the right to withdraw patients from the study for any of the following reasons:

- Concurrent illness
- Occurrence of an unacceptable adverse event (see Individual stopping criteria, above).
- Patient request
- Protocol violations
- Non-compliance
- Administrative reasons
- Failure to return for follow-up

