- General or specific changes in the patient's condition unacceptable for further treatment in the judgment of the investigator

At the time of withdrawal, all study procedures outlined for the End of Study visit should be completed. The primary reason for a patient's withdrawal from the study is to be recorded in the source documents.

Patients who discontinue treatment will be followed for 30 days to capture possible delayed onset AEs.

Safety reporting plan

Safety will be assessed using incidence of all adverse events (AEs), serious adverse events (SAEs), treatment-emergent adverse events (TEAEs) and AEs leading to study withdrawal; review of laboratory data, including hematology, renal function, biochemistry; new concomitant medication usage; hospitalization rates; and vital signs. Adverse events will be classified for serious adverse events using standard regulatory criteria. Other safety endpoints include the incidence of BK nephropathy, opportunistic infections, and malignancies.

Data Confidentiality

A participant's privacy and confidentiality will be respected throughout the study. Each participant will be assigned a unique identification number and these numbers rather than names will be used to collect, store, and report participant information. Site personnel will not transmit documents containing personal health identifiers (PHI) to the study sponsor or their representatives.

Study Documentation

All clinical data is maintained in Microsoft Excel. All study data is downloaded from this database and stored in tables within a separate Microsoft Access file. Study data is output into study files (xls, jmp, doc, ppt, etc.), which are used for summarizing study information. All active study files are stored within a folder on the Transplant Center research server. The investigator is required to ensure that all clinical data is complete for all participants

Study Coordination

Study coordinators will assist in monitoring participant safety, evaluating the progress of the study, and reviewing procedures for maintaining the confidentiality of data and the quality of data collection, management, and analyses.

Preliminary data:

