Safety will be assessed using incidence of all adverse events (AEs), serious adverse events (SAEs), treatment-emergent adverse events (TEAEs) and AEs leading to study withdrawal; review of laboratory data, including hematology, renal function, biochemistry and microbiology and malignancies; new concomitant medication usage; hospitalization rates; and vital signs. Adverse events will be classified for serious adverse events using standard regulatory criteria.

Statistical analysis plan.

Study design and analysis will be performed according to intention to treat principles. Time to development of PTDM will be compared utilizing Kaplan-Meier curves generated according to the product limit method utilizing log-rank tests to evaluate intergroup differences. Risk adjustment for baseline differences between groups will be assessed according to multivariate proportional hazards models. Data on patients who withdraw or are lost to follow-up will be censored at the time of last visit. Comparisons of repeated measures between groups including the secondary endpoints outlined above will be performed utilizing general linear mixed models with transformation of data to logarithm forms when appropriate. These comparisons will be made with inclusion of subjects who withdraw within the follow-up period. Sensitivity analysis excluding these patients will also be performed.

Needed sample size was calculated according to development of PTDM based on utilization of a 2-sided chi-squared test at a 5% significance level and 80% power. The incidence of PTDM reported after kidney transplant varies from 2-50% with best estimates indicating that approximately 30% of patients will develop PTDM.^{3,4,41,42} The SCALE trial comparing GLP-1 receptor agonists to placebo showed an 80% reduction in development of type 2 diabetes.²¹ Other clinical trials evaluating prevention of diabetes showed a 30% risk reduction with metformin and 55-72% reduction with TZDs.^{29,43} Thus, sample size was calculated based on a proportion of 30% incidence of PTDM in the control group and 80% risk reduction in the experimental group (consistent with SCALE trial). A total of 81 (54:27 according to 2:1 randomization) patients will be required to achieve the power and significance levels above. In our preliminary data, 24-33% of kidney transplant recipients meet prediabetes criteria. We would expect that full enrollment would take 24 months.

Data management plan

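### The withdrawal wording blurs stopping exenatide with leaving the study, so diabetes outcomes after drug stopping may be censored, and no planned analysis would show the effect

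*Combined protocol and SAP*

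**What the plan says.** **Separate events, on the face of it.** The list headed "Criteria for Discontinuation of Medication" concerns study drug only. *Study design/schedule* says: "Patients will be followed for 2 years after transplantation (20 or 12 months after enrollment) for progression to all endpoints". The *Statistical analysis plan* declares intention to treat and compares time to diabetes by Kaplan-Meier curves and log-rank tests.

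**Where they merge.**
- *Stopping Rules* says that "the investigator also has the right to withdraw patients from the study for any of the following reasons". One reason is "Occurrence of an unacceptable adverse event (see Individual stopping criteria, above". The only patient-level stopping list above that point is the medication list. Non-compliance is another reason, and the last is a "condition unacceptable for further treatment in the judgment of the investigator", which is a criterion about treatment.
- *Safety/Tolerability Outcomes Measures*, item 3, is titled as adverse events that lead to stopping study medication, but its explanation describes early termination of participation.

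**What follows from withdrawal.** End of Study procedures are done at that time, and the analysis rule applies: "Data on patients who withdraw or are lost to follow-up will be censored at the time of last visit".

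**What is written for drug stoppers.** "Patients who discontinued medication for AEs will be contacted within 30 days to follow up on the resolution of symptoms". A later sentence gives 30 days of follow-up for delayed adverse events. The section on recording adverse events extends serious adverse event reporting to 90 days after the last dose and refers to a follow-up period beyond treatment.

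**Sensitivity analysis.** The repeated-measures comparisons include subjects who withdraw. A sensitivity analysis excluding them comes directly after.

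**The concern.** A site that reads an adverse-event stop as a study withdrawal would censor the patient at the last visit. Another site could keep the same patient in follow-up to 24 months. Both would be within the text. Most withdrawal reasons can arise in either arm, but control patients have no study drug to stop, so this route to censoring exists in one arm only.

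Kaplan-Meier and log-rank methods assume that censored patients have the same later risk as those who remain. If stoppers' risk is higher than stayers', censoring them favours exenatide; if lower, it works against exenatide; if equal, there is no bias. In any of these cases the comparison moves towards an effect in patients who stay on drug, which is not what an intention-to-treat statement leads the reader to expect.

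The loss matters most for patients enrolled at 12 months, about half the trial. As the *Schedule of visits* table reads, their only scheduled HbA1c after enrolment is at Day 730, and censoring before then leaves it out.

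**Working it through.** **1. Reproduce the plan's sample size.** Inputs from the *Statistical analysis plan*: 30% in control, 80% reduction (so 6% on exenatide), two-sided 5%, 80% power, 2:1. The pooled proportion is (0.30 + 2×0.06)/3 = 0.14.

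n(control) = [1.96√(0.14×0.86×1.5) + 0.8416√(0.30×0.70 + 0.06×0.94/2)]² / 0.24² = 26.85, rounded up to 27.

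This gives 27 + 54 = 81, as stated, with power 80.2%.

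**2. Tipping point at planned counts.** The second *Preliminary data* paragraph reports 17% discontinuation among 17 recipients. Used as an assumption, 17% of 54 is about 9 patients, leaving 45 observed. Expected events are 0.30×27 ≈ 8 in control and 0.06×45 ≈ 3 on exenatide. No control patient is censored. The test is the uncorrected chi-squared, z = (p0 − p1)/√[p̄(1 − p̄)(1/n0 + 1/n1)], standing in for the log-rank.

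| Exenatide patients counted | Exenatide events | Control | p |
|---|---|---|---|
| 9 censored patients left out | 3/45 | 8/27 | 0.009 |
| 3 of the 9 diabetic | 6/54 | 8/27 | 0.038 |
| 4 of the 9 diabetic | 7/54 | 8/27 | 0.069 |

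At the control risk of 30%, 0.30×9 = 2.7 of the 9 would be diabetic, so the result just survives.

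**3. Range for the stopping rate.** Read as 3/17, the rate has an exact 95% interval of 4% to 43%, or about 2 to 23 of 54. Observed events are 6% of those remaining, rounded.

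| Censored | Observed | Significance lost when |
|---|---|---|
| 2 | 3/52 | never |
| 5 | 3/49 | 4 of 5 diabetic |
| 9 | 3/45 | 4 of 9 |
| 14 | 2/40 | 5 of 14 (36%) |
| 23 | 2/31 | 5 of 23 (22%) |

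**4. Censoring bias on its own.** Log-rank simulation with no drug effect: 30% risk in both arms, 54:27, and 17% of the exenatide arm censored on stopping. The table gives the share of trials significant at two-sided 5% and favouring exenatide.

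| Stoppers' hazard relative to others | Censored early | Censored halfway |
|---|---|---|
| 1 | 2.9% | 2.9% |
| 1.5 | 4.2% | 3.4% |
| 2 | 5.3% | 3.9% |

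Full follow-up gives about 3% throughout. Counting both directions, total error with censoring is 4.9% at ratio 1, 5.3–5.4% at 1.5, and 5.4% (halfway) or 6.7% (early) at 2.

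**5. The sensitivity analysis.** It follows the repeated-measures sentences, so it is not clear that it reaches the diabetes endpoint. If it does, it removes the same patients and recovers no outcome after withdrawal.

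**The case against.** The strongest reply is that this is a possible misreading and not a rule. The censoring sentence names patients who withdraw or are lost, not those who stop drug. Medication criteria have their own list, and the safety plan names adverse events leading to study withdrawal as a separate item. Follow-up to two years carries no exception for patients off drug. The investigator has a right to withdraw patients, not a duty. A follow-up period beyond treatment is written down, and the repeated-measures comparisons, which include 24-month HbA1c, keep withdrawn subjects. End of Study procedures at withdrawal, if they match the Day 730 column, would include an HbA1c at that point. On size, at 17% stopping the result survives a return to control risk, and only the most extreme simulated case moves the error rate noticeably.

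Most of this stands. A reader might infer that the plan requires drug stoppers to be censored; it does not. A reader might also infer that the trial is biased towards exenatide; the documents do not establish a direction. What remains is that no sentence keeps off-drug patients in diabetes follow-up, while the withdrawal sections give a site grounds to end it. An HbA1c at withdrawal does not show what happens later, and including withdrawn subjects in a mixed model does not recover their diabetes status at 24 months. Intention to treat fixes the arm in which a patient is analysed but does not restore censored outcomes.

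**Conclusion.** The concern holds as a conditional one and should be fixed. Sections that govern the same patients conflict in effect, and one reading drops off-drug outcomes from an analysis declared intention to treat. Bias arises only if adverse-event stoppers are coded as withdrawn and their diabetes risk differs from stayers'. Its size and direction are unknown. In the illustration, one more diabetic patient among nine censored (4, not 3) changes the conclusion. That rests on 17% stopping, no censoring in control, and events at their planned counts. The 17% comes from 17 patients treated for established diabetes, none of whom is said to have left follow-up.

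A reader might go further and charge a lost effect or lost power to the censoring rule. If 17% stop early and return to 30% risk, the all-patient risk is 0.83×0.06 + 0.17×0.30 = 10.1%. The reduction is then 1 − 0.101/0.30 = 66%, not 80%, and power at 81 patients is about 61%. Those figures describe dilution from patients stopping drug. They would appear with complete follow-up and are not a cost of censoring.

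**What to change.** Reconcile *Study design/schedule*, *Stopping Rules*, *Safety/Tolerability Outcomes Measures* and the *Statistical analysis plan*:

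- State that stopping study drug for any reason, or withdrawal from treatment by the investigator (adverse event, non-compliance, protocol violation, administrative), does not by itself end endpoint follow-up.
- Use all standard-of-care glycaemic results to Day 730, including those after drug is stopped.
- Censor the diabetes endpoint only at withdrawal of consent or true loss to follow-up, and state how death before diabetes is handled.
- Record drug stopping and study withdrawal as separate events, each with date and reason. Make the adverse-event cross-reference and safety measure 3 refer clearly to one or the other.
- Keep the existing exclusion analysis for the repeated measures. Add a tipping-point analysis of the diabetes endpoint that varies, in both arms, the number of censored patients counted as diabetic from none to all and reports where the conclusion changes.

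The cost is minor protocol, case-report-form and analysis work. No visits are added, since "The patient visits and follow-up including safety laboratories all fall within the SOC follow-up at all sites". The downside is that the all-patient effect may be less favourable than the planned one. No change to the drug-stopping criteria or to enrolment is proposed.

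### The plan's only between-arm method for death, graft loss and mesangial expansion above 20% is a general linear mixed model, which does not suit rare yes/no outcomes at 2:1 allocation

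*Combined protocol and SAP*

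**What the plan says.** One sentence of the Statistical analysis plan section covers the secondary endpoints: "Comparisons of repeated measures between groups including the secondary endpoints outlined above will be performed utilizing general linear mixed models". It makes taking logs optional, to be done only where suitable. The list it points back to, under Secondary endpoints, has seven items. HbA1c and kidney function ("To compare transplant kidney function in the two arms") are continuous. The other five are events or percentages: progression to diabetes, safety and tolerability, mesangial expansion above 20%, death ("To compare the incidence of death by any cause in the two arms") and graft loss ("To compare the incidence of graft loss by any cause in the two arms").

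Two of those five are provided for elsewhere. Time to diabetes has Kaplan-Meier curves, log-rank tests and proportional hazards models in the same section. Safety is summarised as incidences and as percentages of participants under Safety/Tolerability Outcomes Measures. No further between-arm method is named for death, graft loss or mesangial expansion.

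Adjustment for baseline is mentioned only for the proportional hazards models. The mixed models have no stated covariates, time points or handling of the enrolment value. For kidney function, neither a time point nor a summary measure is given.

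**The concern.** The model is called general, not generalized, and is paired with optional log transformation. That describes a model for continuous outcomes with roughly normal errors. Death and graft loss are single events and are likely to be few among 81 patients. A linear model pools the variance across arms, so when the few events all fall in the smaller control arm the p-value comes out too small. Two deaths under standard care and none on exenatide could then be reported as a significant survival benefit.

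If the sentence was not meant to reach these outcomes, they have no stated comparison at all. In an open-label trial, the test for the gravest outcomes would then be chosen with the results in view.

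Kidney function does suit a mixed model. There, the plan's silence on the enrolment value risks giving up precision that costs nothing to keep, because eGFR is already needed to apply the exclusion criteria.

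**Working it through.** **Inputs from the Statistical analysis plan section.** The sample size rests on a "2-sided chi-squared test at a 5% significance level and 80% power", with "30% incidence of PTDM in the control group and 80% risk reduction in the experimental group", that is 30% against 0.30 × (1 − 0.80) = 6%. "A total of 81 (54:27 according to 2:1 randomization) patients will be required".

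**Inputs assumed, because the documents give none.** Common event risk of 1 to 10% for a rare outcome; correlation r of 0.5 to 0.8 between enrolment and 24-month eGFR.

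**1. The plan's own figure.** With allocation ratio k = 2, the average risk is (0.30 + 2 × 0.06)/3 = 0.14. The control-arm size is

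n = [1.96·√(1.5 × 0.14 × 0.86) + 0.8416·√(0.30 × 0.70 + 0.06 × 0.94/2)]² / 0.24² = (0.833 + 0.411)² / 0.0576 = 26.9.

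This rounds up to 27, so 27 + 54 = 81, with power 80.2%. The stated figure is reproduced.

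**2. Two control events, no exenatide events.** As a stand-in for the linear model, take the pooled-variance two-group t-test on 0/1 data with 79 degrees of freedom.

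- Difference: 2/27 = 0.0741.
- Pooled variance: 2 × (25/27)/79 = 0.02344.
- Standard error: √(0.02344 × (1/27 + 1/54)) = 0.0361.
- t = 0.0741/0.0361 = 2.05, p = 0.043.
- Fisher: C(27,2)/C(81,2) = 351/3240 = 0.108. The other two possible splits are more probable, so nothing is added for the second side.

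The same calculation for other splits:

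| Events, control (of 27) vs exenatide (of 54) | Linear p | Fisher p |
|---|---|---|
| 2 vs 0 | 0.043 | 0.108 |
| 3 vs 0 | 0.012 | 0.034 |
| 0 vs 7 | 0.051 | 0.089 |
| 0 vs 8 | 0.035 | 0.047 |

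**3. How often chance alone gives a false claim.** For every pair of event counts, multiply the two binomial probabilities under the same risk in both arms, and add up the pairs with two-sided p < 0.05.

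| Common risk (assumed) | Linear, favours exenatide | Linear, favours control | Fisher, favours exenatide | Fisher, favours control |
|---|---|---|---|---|
| 1% | 1.7% | <0.01% | 0.15% | <0.01% |
| 2% | 3.5% | <0.01% | 0.6% | <0.01% |
| 3% | 4.0% | 0.01% | 1.2% | 0.01% |
| 5% | 3.5% | 0.13% | 2.0% | 0.13% |
| 10% | 2.7% | 1.3% | 2.0% | 1.0% |

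A hand check at 2%: no exenatide events has probability 0.98⁵⁴ = 0.336, and two or more control events 0.101. Their product is 0.034, which is nearly all of the 3.5%.

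**4. Baseline eGFR.** Simplify to a single 24-month value. The difference detectable with 80% power is 2.80 × √(1/27 + 1/54) = 0.66 SD without baseline. With baseline as a covariate the variance is multiplied by 1 − r². At r = 0.5 it falls by 25% and the detectable difference is 0.66 × √0.75 = 0.57 SD. At r = 0.8 it falls by 64% and the difference is 0.66 × √0.36 = 0.40 SD.

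**The case against.** The strongest reply is that the sentence opens with repeated measures, and death is not one. It may be loose drafting, and normal errors are inferred from the word general. That is fair, but it does not remove the gap: on that reading death, graft loss and mesangial expansion have no stated comparison. The t-test is also only a stand-in for whatever mixed model would be fitted.

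Several stronger readings are tempting, and the documents or the numbers do not support them.

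- **That the plan takes logs of 0/1 data.** Transformation is only where appropriate; nothing asks for it on event outcomes.
- **That no event-type endpoint has a method.** Progression to diabetes has log-rank and proportional hazards, and safety is summarised by percentages. The section on potential challenges also puts significance testing of longitudinal biopsy changes outside the trial's reach, so mesangial expansion may be mainly descriptive.
- **That overall type I error is inflated.** Adding the two linear columns above gives at most about 4.0%, below the nominal 5%. What is left is the direction of the error and the 2 versus 0 case.
- **That the linear model would miss harm which Fisher would catch.** With no control events, both tests first reject at 8 exenatide events, and at 7 Fisher is further from significance. At assumed risks of 2% against 15%, power to detect harm is 39% linear and 35% Fisher. The asymmetry comes mainly from 2:1 allocation and few events, and Fisher shares it.
- **That baseline eGFR is excluded.** The plan is silent. A repeated-measures model could take the enrolment value as its first response, so the loss of precision is conditional.

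**Conclusion.** The point holds in a limited form. As written, three yes/no secondary endpoints have either an unsuitable linear model or no specified comparison. The clearest consequence is that 2 control events against none would count as significant. At assumed common risks of 2 to 5%, false findings in exenatide's favour are about two to six times as frequent as with Fisher (3.5/2.0 = 1.8 at 5%; 3.5/0.6 = 5.8 at 2%). This rests on the assumed event risks, full enrolment at 27:54 and the t-test stand-in. The gain from using baseline eGFR rests on the assumed correlation and the single-value simplification; creatinine is in fact measured repeatedly.

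A reader might infer that the trial's main conclusion is at risk. It is not: the primary analysis uses other methods, and the 81 patients follow from the plan's own inputs. The SAP should be amended, but the design need not change.

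**What to change.** Replace the sentence in the Statistical analysis plan section with methods by endpoint type.

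- **eGFR and HbA1c:** mixed models, with enrolment cohort (4 or 12 months) as a covariate. For kidney function, add enrolment eGFR as a covariate or as the first response.
- **Enrolment HbA1c:** add it once the documents agree on whether it is measured. Study design/schedule places HbA1c at 4, 12 and 24 months, but both tables under Schedule of visits leave it unmarked at enrolment, and eligibility can rest on glucose alone.
- **Mesangial expansion above 20%, and any safety percentages that are tested:** Fisher's exact test, or exact Cochran-Mantel-Haenszel by cohort, with risk differences and exact 95% confidence intervals. The intervals will show how little a few events can exclude.
- **Death and graft loss:** exact or cohort-stratified time-to-event methods that allow for follow-up of 20 or 12 months and for withdrawals. State whether death counts as graft loss; if not, treat it as a competing event.

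The cost is SAP wording. No new data are needed, except possibly an enrolment HbA1c if the reconciliation shows that it is not being collected.
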